5.2. Protocol Deviations

A protocol deviation is defined as non-compliance with the protocol/ICH-GCP which may impact subject rights, safety or well-being, or the integrity of the data:

- Significant Deviation: Non-compliance with the protocol/ICH-GCP which significantly impacts subject rights, safety or well-being, or the integrity of the data.
- Non-Significant Deviation - Non-compliance with the protocol/ICH-GCP which does not significantly impact subject rights, safety or well-being, or the integrity of the data.

All potential significant protocol deviations will be discussed and reviewed on a case-by-case basis.

Protocol deviation significance will be assessed based on the guidelines provided in GSK RAD201677 Standard Guidelines Protocol Variances.

As the study is ongoing, additional significant protocol deviations can also be spontaneously identified or defined during trending and review of protocol deviations by GlaxoSmithKline (GSK) and/or PPD teams during the regularly planned study deviation review meetings and the significant Protocol Deviations Rules document will be updated. More details of the process are provided in the Protocol Deviations Monitoring Plan (PDMP).

Prior to database lock, all protocol deviations will be revised, categorized and assessed as to significance.

Significant protocol deviations will be summarized by treatment in a table and all protocol deviations, significant and non-significant, will be presented in a listing. The subject data listing will be sorted by deviation type, treatment group, site and subject number.

6. Demographics and Baseline Characteristics

Unless otherwise specified, all tables and listings in this section will be based on the randomized set, and all summaries and data listings will use treatment labels as specified in [Section 3.3](#).

6.1. Demographics

The demographic characteristics (age, race, ethnicity, sex, as well as Baseline height, body weight and BMI) will be summarized by treatment group. Age, height and weight will be summarized using the mean, standard deviation, median, minimum and maximum. In addition, age will also be categorized and summarized by $\geq 50-64$, $\geq 65-74$, $\geq 75-84$ and ≥ 85 years. The number and percentage of subjects by age category, sex and ethnicity will be computed using the categories as provided in the eCRF. All demographic data, including female child-bearing potential will also be presented in a listing.

The proportion of subjects in each of the 3 age ranges will also be summarized (but not listed): Adult (18-64 years); $\geq 65-84$ years; ≥ 85 years.

A summary of race and racial combinations will be presented overall and by treatment group. The number and percentage of subjects by race will be reported. As a subject could have more than 1 race, the number and percentage of subjects with multiple races will also be reported. Percentages will be based on the total number of subjects in the Randomized set. All data will be listed in detail.

A specific listing displaying informed consent information will be produced.

6.2. Disease Characteristics

6.2.1. GCA Diagnosis and Disease Activity at Screening

Giant cell arteritis diagnosis at Screening will be summarized. This table includes:

- Time since formal diagnosis,
- Time since suspected diagnosis,
- Disease type (new onset or relapsing/refractory)
- Type of diagnosis
 - Temporal artery biopsy performed
 - Temporal artery ultrasound (TA US) performed
 - Angiography or cross-sectional imaging performed
- Acute-phase proteins (Screening CRP < 1mg/dL and ESR < 30mm/hr)
- Signs and symptoms present for the diagnosis
- Disease activity at screening: recorded in the eCRF page GCA Disease Activity (Screening): cranial signs or symptoms, symptoms of PMR, other signs or symptoms attributable to GCA or PMR flares, and visual signs or symptoms.

All information related to GCA diagnosis and GCA disease activity will be listed separately in detail.

Specific rules regarding imputation of missing or partial dates are provided in [Section 4.6.4](#).

6.2.2. Disease Characteristics of GCA at Baseline

The following variables will be summarized:

- Baseline prednisone dose (stratification factor)
- Acute-phase proteins (Baseline CRP < 1mg/dL and ESR < 30mm/hr)
- Remission status: clinical remission at Baseline and normalization of CRP and ESR. A subject in clinical remission is a subject that does not have any signs and symptoms, which is also determined by a lack of flare. If a subject does have a flare, they will have one or more signs and symptoms, and therefore are not considered as being in clinical remission. A subject without any flare at the Baseline visit will be considered in clinical remission.
- Baseline Patient's Global Assessment of Disease Activity VAS
- Baseline signs and symptoms: cranial signs or symptoms, symptoms of PMR, other signs or symptoms attributable to GCA or PMR flares, and visual signs or symptoms.

All data will be listed in detail.

6.3. Medical History

6.3.1. General Medical History

Relevant medical history will be summarized by number and percent of subjects by the following medical condition categories for current and past conditions separately:

- Cardiovascular Risk Factors
- Musculoskeletal and Connective Tissue Disorders
- Blood and Lymphatic System Disorders

- Eye Disorders
- Psychological Disorders
- Endocrine Disorders
- Metabolism and Nutrition Disorders
- Infection and Infestations
- Gastrointestinal Disorders
- Renal Disorders
- Urinary Tract

All medical history information will be listed in detail.

6.3.2. Disease-Specific History

Cardiovascular medical history and risk factors including are assessed at Screening. Cardiovascular risk assessment results will be listed which include: tobacco history (i.e. never smoked, current smoker, and former smoker), family history and medical/surgical procedures.

6.4. Inclusion and Exclusion Criteria

All study inclusion and exclusion criteria are presented in Sections 5.1 and 5.2 of the study protocol. All inclusion and exclusion criteria will be listed separately, using the all subjects screened set. Criteria under different protocol versions will be included in the listings.

The screening status (enrolled / failed) and reasons for screen failure will be summarized and listed using the all subjects screened set. The top 4 reasons for failing inclusion/exclusion criteria will be included in the summary. Percentages for reasons will be based on all subjects screened.

7. Treatments and Medications

7.1. Prior and Concomitant Medications

Prior and concomitant medications are recorded on 3 different concomitant medications eCRF pages:

- Prior Concomitant Medications form
- Concomitant Medications – Non-Corticosteroids
- Concomitant Medications – Corticosteroids

Prior and concomitant medications will be coded using GSK Drug coding dictionary, summarized separately on the Safety set and each summary will be split by corticosteroids and non-corticosteroids. All prior and concomitant medications will be listed for the Safety set.

In this study, prior medications are defined as those medications with a recorded start date prior to the initiation of SC IP. Prior medications are collected at Screening and are noted as to whether they are cardiovascular, GCA related, non-GCA related or corticosteroid medications.

Concomitant medications for Part A are defined as those medications which are taken on or after the initiation of SC IP in Part A, up to the Week 52 visit or the first SC IP of Part B open-label treatment, whichever is earlier for subjects participating in Part B.

Concomitant medications taken during the 16-weeks Safety follow-up visit will be summarized in Part A or Part B as relevant.

Concomitant medications where the eCRF option “Was drug administered as a rescue medication” is selected as “Yes” and that are corticosteroids when the unit is not in (Actuation, Application, Area under curve, Cubic centimeter, Cells, Cells per kilogram, Fingertip unit, Drops, Gum, Inhalation, Kilocalories, Minimum alveolar concentration, Mega becquerels (MBq), Millicurie, Nebule, Patch, Powder, Puff, Ring, Spray, suppository) or non-corticosteroid and GCA related will be considered as rescue therapies.

Three summary tables will be displayed:

- Prior medications
- Concomitant medications – rescue therapies
- Concomitant medications – non-rescue therapies

A listing of all rescue medications will be produced.

Each of the 3 summary table will be split by medication type: corticosteroids or non-corticosteroids. Within each byline, medications will be presented in the descending order of total incidence (i.e., summed across all treatment groups) by Anatomical Therapeutic Chemical (ATC) level 1 and ingredient for the Safety set.

Multi-ingredient products will be summarized by their separate ingredients rather than as a combination of ingredients. For incidence reporting, if a subject took more than 1 concomitant medication that was coded to the same ATC level 1 or ingredient, the subject will only be counted once for the respective ATC classification or ingredient in the summary. A medication could be mapped to several ATC terms. In this case it will be displayed under all the ATC terms mapped. However, medications mapped to several ATC terms will be counted once when deriving cumulative prednisone dose.

Specific rules regarding imputation of missing or partial dates are provided in [Section 4.6.4](#).

If start date is completely missing and end date is after first dose intake or completely missing, then the medication will be classified as both prior and concomitant. If the start date is completely missing and the end date is prior to the first dose of study drug, then the medication will be classified as prior. If the end date is missing and the start date is after first dose intake, then the medication will be considered as ongoing and classified as concomitant. If the end date is missing and the start date is before first dose intake, then the medication will be considered as ongoing and classified as both prior and concomitant.

Medications with start and stop dates either side of Part A first SC IP dose date will be summarized as both prior and concomitant medications.

7.2. Study Treatments

7.2.1. Extent of Exposure

Listings of exposure to SC IP and prednisone study drug will be provided.

A summary of SC IP exposure will be provided. The following 3 parameters will be reported on the Safety set:

- Total number of injections a subject receives.
- Duration of SC IP treatment (weeks): defined as (Date of last SC IP dose – Date of first SC IP dose + 1 day) / 7. Only complete dates will be used when calculating duration of treatment. First and last injection dates will be used, regardless of any missed doses.
- Duration of SC IP exposure (weeks): defined as (Date of last SC IP dose – Date of first SC IP dose + 112 days) / 7, where 112 days corresponds to 16 weeks. Only complete dates will be used when calculating duration of exposure. First and last injection dates will be used, regardless of any missed doses.
- Cumulative SC IP dose: defined as the total dose in mg (SC IP or placebo) a subject receives.

A summary of prednisone study drug exposure will be provided. The following 2 parameters will be reported on the Safety set:

- Duration of prednisone study drug treatment (weeks): defined as (Date of last non-zero dose from the taper [i.e. the last prednisone end date from taper with a non-zero dose recorded] – Date of first dose from the taper + 1 day) / 7.
- Cumulative prednisone study drug dose (mg): defined as the total dose in mg a subject receives. For each week of the taper (both open-label and blinded), cumulative dose will be calculated as: the number of days x expected doses, the expected dose depending on the pre-specified taper schedule. Overall cumulative dose will be the sum of the cumulative doses of each week.

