GSK	GlaxoSmithKline
HAQ-DI	Health Assessment Questionnaire – Disability Index
ICH E9	International Council for Harmonization Efficacy guideline 9
IDMC	Independent Data Monitoring Committee
IFN	Interferon
IL	Interleukin
IP	Investigational Product
ITT	Intent-to-Treat
MACE	Major Adverse Cardiac Events

MCS	Mental Component Summary
MedDRA	Medical Dictionary for Regulatory Activities
MMRM	Mixed Model for Repeated Measures
NRS	Numeric Rating Scale
P1NP	Procollagen Type 1 N-propeptide
PCI	Potential Clinical Importance
PCS	Physical Component Summary
PD	Pharmacodynamics
PGIC	Patient Global Impression of Change
PH	Proportional Hazards
PK	Pharmacokinetics
PMR	Polymyalgia Rheumatica
PP	Per Protocol
PT	Preferred Term
PhGA	Physician Global Assessment of disease activity
PtGA	Patient Global Assessment of disease activity
PRO	Patient-Reported Outcomes
q2w	Every 2 weeks
q4w	Every 4 weeks
SAE	Serious Adverse Event
SAP	Statistical Analysis Plan
SAS	Statistical Analysis System
SC	Subcutaneous
SD	Standard Deviation
SE	Standard Error
SIQ	Steroid Impact Questionnaire
SF-36v2	36-item Short Form health survey version 2
SMQ	Standardized MedDRA Query
SOC	System Organ Class
TEAE	Treatment-Emergent Adverse Event
TEAESI	Treatment-Emergent Adverse Event of Special Interest

US	Ultrasound
VAS	Visual Analogue Scale

1. Introduction

Sirukumab is a human anti-interleukin (IL)-6 immunoglobulin G1 (IgG1) kappa monoclonal antibody with a high affinity and specificity for binding to the human IL-6 molecule that is being developed for the treatment of giant cell arteritis (GCA).

Multiple lines of evidence support a role for IL-6 in the pathophysiology of GCA. Sirukumab may have therapeutic benefit in the treatment of GCA by interruption of multiple pathogenic pathways. The purpose of this study is to evaluate the efficacy and safety of sirukumab to characterize the benefit-to-risk profile of sirukumab in the treatment of active GCA.

This Statistical Analysis Plan (SAP) is based on the protocol version 3.0 dated of 17th November 2016. This SAP contains definitions of analysis sets, derived variables and statistical methods for the analyses of efficacy and safety endpoints.

[Section 4](#) to [Section 10](#) focus on Part A of this study. Specific derivations for Part B will be presented in [Section 11](#).

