9.1. Adverse Events

The definition of an AE is detailed in Section 12.4.1 in Appendix 4 of the protocol.

Treatment-emergent AEs:

A treatment-emergent AE for Part A is defined as an AE with a start date during the exposed period.

The exposed period is defined as the period from the 1st dose of SC IP to:

- Early withdrawal: last dose of SC IP + 16 weeks

- Completers (subjects who attended the week 52 visit):
 - Week 52 visit if entering into part B
 - Last dose of SC IP + 16 weeks if not entering into part B

Unless otherwise specified, AE outputs will be based on TEAEs.

All AEs will be coded by system organ class (SOC) and preferred term (PT) according to the Medical Dictionary for Regulatory Activities (MedDRA, Version 19.0 or higher).

An overview summary of TEAEs, including counts and percentages of subjects will be generated by actual treatment group, with any of the following categories:

- Any TEAE, TEAEs related to study treatment (SC IP and/or prednisone study drug), TEAEs leading to permanent discontinuation of study treatment, TEAEs leading to dose interruption/delay, TEAEs leading to dose reduction, TEAEs leading to dose increase, TEAEs leading to dose not changed.
- Any serious TEAEs, serious TEAEs related to study treatment (SC IP and/or prednisone study drug), fatal serious TEAEs, and fatal serious TEAEs related to study treatment.
- Any TEAE of special interest (TEAESI) (see [section 9.1.8](#) for further details), TEAESIs related to study treatments (SC IP and/or prednisone study drug), TEAESIs leading to permanent discontinuation of study treatment, TEAESIs leading to dose reduction, TEAESIs leading to dose increase, TEAESIs leading to dose not changed, TEAESIs leading to dose interruption/delay.

A listing presenting the relationship between SOC, PT, and AE reported will be provided.

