11.2. Extent of Exposure

The following 3 parameters will be reported on the Safety set:

- Total number of injections a subject receives during Part B.

- Duration of SC IP treatment (weeks): defined as (Date of last SC IP dose in Part B – Date of first SC IP dose in Part B + 1 day) / 7. Only complete dates will be used when calculating duration of treatment. First and last injection dates will be used, regardless of any missed doses.
- Duration of SC IP exposure (weeks): defined as (Date of last SC IP dose in Part B – Date of first SC IP dose in Part B + 112 days) / 7. Only complete dates will be used when calculating duration of exposure. First and last injection dates will be used, regardless of any missed doses.
- Cumulative SC IP dose: defined as the total dose in mg a subject receives during Part B.

No compliance will be calculated for Part B.

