11.4.2. Endpoints from Part A Reported during Part B

The following efficacy endpoints will be summarized and listed for Part B as for Part A using the by-line as specified in [Section 11](#), unless otherwise specified. The visit displayed in the outputs will be the re-mapped visit as specified in [Section 11.5](#).

- Cumulative prednisone dose over time:
Derivation will be the same as for Part A, as described in [Section 8.2.1](#). Only corticosteroid rescue therapies, as defined in [Section 3.3](#) and [Section 7.3](#) will be taken into account in the derivation of cumulative prednisone dose over time. All medication taken the day after the Week 52 visit of Part A will be considered in the analysis.
An additional summary will be displayed taking into account prednisone dose taken during both Part A and Part B.
- Number of disease flares per subject over time:

Derivation will be the same as for Part A, as described in [Section 8.2.4](#). All events occurring the day after the Week 52 visit of Part A will be considered in the analysis. The summary table will not use the Part B by-line.

An additional summary will be displayed taking into account all flares occurring during both Part A and Part B.

- Proportion of subjects requiring hospitalizations for disease flare and number of hospitalizations for disease flare over time:
Derivation will be the same as for Part A, as described in [Section 8.2.5](#). All events occurring the day after the Week 52 visit of Part A will be considered in the analysis. The summary table will not use the Part B by-line
- Patient-reported outcomes including SF-36v2 acute, EQ-5D (5L), FACIT-Fatigue, Pain NRS, Steroid Impact Questionnaire, HAQ-DI, PtGA and PhGA are exploratory endpoints in Part B and will only be listed

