11.5. Adverse Events

Since some subjects may not take any study drug during Part B, all AEs (not only TEAEs) will be summarized for Part B. An AE for Part B is defined as an AE starting from the Part A Week 52 visit date or the first SC IP of the Part B open-label treatment, whichever is earlier, to the end of study.

All adverse events summary table will be duplicated:

- The first table will use the byline: “Never Received OL Sirukumab during Part B” vs. “Received at Least 1 Dose of OL Sirukumab during Part B”
- The second table will use the following byline:
 - “Exposed” adverse events: Defined as all AEs occurring within 16 weeks after Sirukumab (SC IP or OL Sirukumab intake during Part B)
 - “Non-exposed” adverse events: Defined as all AEs not occurring within 16 weeks after Sirukumab (SC IP or OL Sirukumab intake during Part B)

It is important to note that all adverse events occurring during Part B within 16 weeks after the last intake of SC IP will be considered as “Exposed”, even if a subject never took OL Sirukumab during Part B.

No adverse events leading to discontinuation of study that is related to prednisone study drug will be displayed since prednisone study drug is only taken during Part A. TEAE related to prednisone will be displayed for Part B (instead of related to prednisone study drug for Part A).

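### Part A exposure is not cut off at the first open-label dose and the Week 52 date sits in both adverse-event windows, so some exposure time and some events appear in both parts' tables.

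*SAP*

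**What the plan says.** **Exposure.** The SAP introduction states that Sections 4 to 10 "focus on Part A of this study". Within that range, 7.2.1 computes duration of SC exposure as "Date of last SC IP dose – Date of first SC IP dose + 112 days", divided by 7, "where 112 days corresponds to 16 weeks". It makes no exception for subjects who enter Part B or start open-label drug. Section 11.2 computes Part B exposure as "Date of last SC IP dose in Part B – Date of first SC IP dose in Part B + 112 days", again divided by 7.

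**Adverse events.** Section 9.1 starts the Part A exposed period at the first SC dose. For subjects who attend Week 52 it ends at "Week 52 visit if entering into part B". In Part B, 11.5 says: "An AE for Part B is defined as an AE starting from the Part A Week 52 visit date", or from the first open-label dose if that is earlier.

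**Nearby rules.** Section 7.1 closes Part A concomitant medications at the Week 52 visit or the first open-label dose, whichever comes first. For Part B flares and hospitalizations, 11.4.2 uses a later start than 11.5: "All events occurring the day after the Week 52 visit of Part A will be considered in the analysis". Prednisone follows the same rule.

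**The concern.** Two exposure clocks run at once for anyone who starts open-label drug before the Part A tail has expired. The Part A table then claims time that the Part B table also claims. For a subject from Arm D or E, the Part A table files that time under placebo although the drug being given is sirukumab. The AE windows also meet on a shared date rather than on consecutive dates. Week 52 is also the visit at which open-label drug is dispensed to immediate starters, so a reaction to the first open-label injection that day would be listed under the blinded arm as well as in Part B.

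Extent of exposure is the background against which safety tables are read. Section 11 says the Part A safety summaries will be repeated for Part B. Each part's table should therefore hold its own time and its own events.

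**Working it through.** **Inputs**
- Tail: 112 days (7.2.1 and 11.2). Check: 112/7 = 16 weeks, as the SAP states.
- First blinded dose: day 0. Week 52 visit: day 364.
- Last blinded dose: Week 50 (day 350). This is an assumption from q2w dosing and from Table 10, footnote 3, which limits Week 52 dispensing to open-label starters. The compliance example in 7.2.2.1 counts an injection on the last visit day (Week 20 gives 11), so Week 52 (day 364) is shown as the upper end.
- A full year of open-label dosing: last dose 350 days after the first.

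**Immediate open-label starter, last blinded dose Week 50**
- Part A, 7.2.1: (350 − 0 + 112)/7 = 66 weeks
- Part B, 11.2: (350 + 112)/7 = 66 weeks
- Sum: 132 weeks
- Calendar span: (364 + 350 + 112)/7 = 118 weeks
- In both tables: 132 − 118 = 14 weeks, and 14/118 = 11.9%

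The 14 weeks do not depend on a full year of open-label drug. With a single open-label dose, Part B is 112/7 = 16 weeks, the sum is 66 + 16 = 82, and the calendar span is (364 + 112)/7 = 68. The overlap is again 14.

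**Later open-label starts.** Overlap = (last blinded dose + 112 − first open-label dose)/7, with a minimum of zero.

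| Open-label start (Part B week) | Last blinded dose Week 50 | Last blinded dose Week 52 |
|---|---|---|
| 0 | 14 weeks | 16 weeks |
| 4 | 10 | 12 |
| 12 | 2 | 4 |
| 14 | 0 | 2 |
| 16 | 0 | 0 |

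**Adverse-event windows.** With the visit day included, Part A covers days 0 to 364 and Part B starts at day 364, so they share one calendar day. If the first open-label dose comes d days before the visit, they share d + 1 days.

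**After the repair.** Counting days inclusively, Part A exposure becomes the smaller of (last − first + 112) and (first open-label dose − first dose). For the immediate starter that is min(462, 364)/7 = 52 weeks, and 52 + 66 = 118, the calendar span. With exclusive AE boundaries the shared days fall to zero.

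**The case against.** **The tail is deliberate.** A reader might infer that 66 weeks is simply too long for every completer entering Part B, since 9.1 stops at Week 52 and 14/52 = 27%. The documents do not support that. Under 11.5, Part B events within 16 weeks of the last SC dose count as exposed even when no open-label drug was taken, and the Protocol (4.1) sets a 16-week safety period after the last dose. For a subject in remission who stops blinded drug on entering Part B, 66 weeks fits the SAP's own concept. This part of the objection stands and confines the exposure point to early open-label starters.

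**No rate is inflated.** A reader might infer that AE incidence per 100 subject-years is distorted. It is not: 9.1.1 takes person-time from the 9.1 exposed period, which ends at Week 52 for Part B entrants, and not from the 7.2.1 duration. This stands.

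**Nothing is added up.** The 132-week total is never produced. Combined Part A and Part B summaries are specified only for prednisone and flares, which already start Part B on the day after. Treatment duration without the tail, number of injections and cumulative dose are reported alongside. All true. The duplication means presence in both parts' tables, not a wrong total.

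**Few subjects.** SAP 1.1 says that few subjects completed Week 52 before termination. That limits how many can be affected, though not what the rule does to each of them.

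**Conclusion.** The point holds for descriptive tables only. For subjects who start open-label sirukumab within about 14 weeks of Part B entry (about 16 if the last blinded dose is at Week 52), the same calendar time appears in both parts' exposure summaries. It is largest for an immediate starter, at 14 weeks (16 with a Week 52 dose). In Arms D and E it is labelled placebo exposure.

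The AE overlap covers events that start on the Week 52 visit date, or between an earlier first open-label dose and that visit. It does not extend to everything recorded at the Week 52 visit, as a reader might infer.

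The sizes assume nominal dosing dates. The shared AE day assumes that the 9.1 period includes the visit day. Section 9.1 does not say so, but 4.4 counts the visit day in the interval ending at that visit. If 9.1 meant to exclude it, the text should say so. The documents do not give the number of subjects affected.

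**What to change.** 1. **Section 7.2.1.** End Part A exposure at the earlier of the last Part A dose + 112 days and the day before the first open-label dose. Keep the full tail for Part B entrants never given open-label drug.
2. **Sections 9.1 and 11.5, same cut in both.** For subjects with an open-label dose on or before the Week 52 visit date, AEs starting on or after that first dose date count only in Part B. For all others, AEs starting on the Week 52 date count only in Part A, and Part B begins the next day.

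Two simpler repairs would each do harm. Capping every Part B entrant at Week 52 would remove 14 weeks from subjects never given open-label drug. Section 11.2 gives them no Part B exposure in return, yet 11.5 still classes their events as exposed. Starting all Part B AEs the day after Week 52 would leave a same-day reaction to a first open-label dose only under the blinded arm, placebo included.

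Cost: two derivations change and no new data are needed. Reported Part A exposure becomes shorter for early open-label starters. An event that begins on the day of the first open-label dose but before the injection would go to Part B, a small price for a rule based on dates alone.
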